6.2 Determination of Sample Size and Accrual Rate

6.2.1 Sample Size and Power Estimate

We expect that the clinical volume of 30 patients/month for 12 months will yield a potential enrollment pool of 360 patients. Anticipating a 30% decline, dropout, or ineligibility rate at the time of potential enrollment, then at least 250 patients should be evaluable. The sample size was determined based on the primary outcomes of changes in practice patterns. For each disease stage, a test of at least a 25% improvement using the decision aid compared with the pre-intervention results in the proportion of patients satisfying the stage-specific criterion listed above will be carried out (see Primary Endpoint for practice pattern metrics). In addition, the entire study sample will be evaluated to test for a change in smoking cessation plans. Patients will be included in up to 3 individual analyses. The maximum sample size for any one test is based upon assuming a null hypothesis of 50% in the pre-intervention cohort. This estimate for the null hypothesis will be modified using the results obtained prior to use of the decision aid (Months 1-8). Based upon the one-sample binary exact test with power set at 90% and a 2-sided type I error of 0.017 (adjusted for up to 3 tests for all patients), 53 patients would be required for each test. The test would reflect the actual accrual by stage with the use of the decision aid. With a fixed type I error of 0.017, this means for any individual test that the sample size may differ from 53, and the null hypothesis may differ from 50% and result in reduced power but will be at least 80%. For example, if adjuvant chemotherapy is given after surgery to 40% of stage IB and II patients determined from the pre-intervention assessment, then a test to detect a 50% improvement to 60% will require 70 patients with 80% power and 88 patients with 91% power. Similarly, if 60% of patients satisfy the smoking cessation criterion during the

pre-intervention interval, a 50% improvement will require 32 patients with 92% power, but a 15% improvement with 90% power requires 135 patients across all disease stages. It is therefore not anticipated that the comparisons will require more than the expected enrollment of 250 patients.

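### Section 6.2.1 promises at least 80% power for every test without tying it to group size, and expresses improvement on two scales, so the target after the null is reset is unclear

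*Combined protocol and SAP*

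**What the plan says.** All of this is in section 6.2.1 unless noted.

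- Target: "For each disease stage, a test of at least a 25% improvement using the decision aid compared with the pre-intervention results" is planned, and the whole sample is tested for smoking cessation.
- Test: "Based upon the one-sample binary exact test with power set at 90% and a 2-sided type I error of 0.017", which gives 53 patients per test.
- Null: "The maximum sample size for any one test is based upon assuming a null hypothesis of 50% in the pre-intervention cohort". It is then replaced: "This estimate for the null hypothesis will be modified using the results obtained prior to use of the decision aid (Months 1-8").
- Group size: "The test would reflect the actual accrual by stage with the use of the decision aid".
- Floor: the sample size may depart from 53, and "the null hypothesis may differ from 50% and result in reduced power but will be at least 80" per cent.
- Examples: for adjuvant chemotherapy at a 40% baseline, "then a test to detect a 50% improvement to 60% will require 70 patients with 80% power" (and 88 with 91%). For smoking cessation at a 60% baseline, "a 50% improvement will require 32 patients with 92% power, but a 15% improvement with 90% power requires 135 patients across all disease stages".
- Feasibility: the section closes by comparing these requirements with the expected total of 250.

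Sections 2.1 and 6.1.1 define the six practice patterns. Smoking cessation applies to everyone. The other five use four non-overlapping groups: stage IB-IIB with surgery, stage III with surgery, stage III without surgery (two tests) and stage IV. No section gives an expected stage or surgery mix, a quota, a minimum group size or a rule for a group that falls short.

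**The concern.** Two features of the paragraph do not fit together.

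First, the 80% floor carries no condition, although the paragraph leaves open both quantities that determine power: the group size and the null rate. The only support offered is a comparison with 250, but a stage test does not draw on 250 patients. It draws on its own group. A non-significant result in a small stage group could then be read as coming from an adequately powered test when it did not.

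Second, the size of improvement to be detected is not on one scale. This is harmless while each example stands alone. It matters once the null is replaced by the Months 1-8 rate, because the target rate must then be derived from the text, and the text allows two answers with very different sample sizes.

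**Working it through.** **Inputs (section 6.2.1).** One-sample exact binomial test, two-sided alpha 0.017 (0.05/3 = 0.0167), null p0, target p1, group size n. The two-sided convention is not stated, so two were used:

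- Equal tails: the critical value c is the smallest integer with P(X ≥ c | n, p0) ≤ 0.017/2 = 0.0085. Power is P(X ≥ c | n, p1); the lower tail adds nothing visible.
- Minimum likelihood: the p-value is the sum of all null probabilities no larger than that of the observed count; reject if it is ≤ 0.017.

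**Step 1: the plan's own figures.** Both conventions give the same values.

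| n | p0 to p1 | c | Power | Plan states |
|---|---|---|---|---|
| 53 | 50 to 75 | 36 | 90.8% | 90% |
| 70 | 40 to 60 | 39 | 80.4% | 80% |
| 88 | 40 to 60 | 47 | 91.4% | 91% |
| 135 | 60 to 75 | 95 | 90.8% | 90% |
| 32 | 60 to 90 | 27 | 90.6% | 92% |

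The sizes are sound. The last power is slightly off; n = 31 gives 91.7%.

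**Step 2: which scale each figure needs.** Read as relative gains, the 25% case is 50 × 1.25 = 62.5%, with 25% power at n = 53, and the 15% case is 60 × 1.15 = 69%, with 41% power at n = 135. These two are therefore absolute points. The two 50% cases are relative: 40 × 1.5 = 60% and 60 × 1.5 = 90% (an absolute reading of the second would be 110%).

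**Step 3: the floor against group size.** For 50 to 75, with small group sizes assumed for illustration (both conventions agree):

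| n | 20 | 25 | 30 | 40 | 41 | 42 | 43 |
|---|---|---|---|---|---|---|---|
| Power | 41% | 56% | 67% | 82.1% | 79.4% | 76.6% | 83.4% |

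Exact power is saw-toothed. It first reaches 80% at 40 and stays there from 43.

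For the plan's 40 to 60 example, power at n = 53 is 64.5% (equal tails) or 74.2% (minimum likelihood). If all 250 patients fell evenly into the four groups (an assumption; 250/4 = 62.5), power would be 75.9% at n = 62 under both conventions, and 72.5% or 80.3% at n = 63.

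For 25-point gains the floor does hold at n = 53: 87.2% or 92.1% for 40 to 65, 90.8% for 50 to 75, and 95.4% for 60 to 85.

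**Step 4: sizes for 80% power.**

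| p0 to p1 | First reached, equal tails | Assured from (both conventions) |
|---|---|---|
| 50 to 75 | 40 | 43 |
| 40 to 65 | 42 | 44 |
| 60 to 85 | 36 | 39 |
| 40 to 60 | 67 | 69 |

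**Step 5: the two readings after a reset.** Ranges run from the first n that reaches 80% to the n from which it is assured, over both conventions.

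| Baseline | 25 points | 25% relative |
|---|---|---|
| 40% | to 65%: 42 to 44 | to 50%: 257 to 267 |
| 50% | to 75%: 40 to 43 | to 62.5%: 166 to 175 |

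From a 40% null with n = 53, power is 87.2% or 92.1% for a target of 65%, and 13.6% or 20.5% for a target of 50%. With all 250 patients, 40 to 50 has 75.7% or 79.5%.

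**The case against.** The floor can be read more mildly. The sentence that follows it ties 80% to a required number of patients, as a planning criterion would: enough patients will be found to reach 80%. That reading is possible. But the preceding sentence says that each test takes whatever accrues by stage, and the section shows nothing that would secure the required numbers. The condition still has to be written down.

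On the scale, each worked example has one identifiable target: 60% is printed in the first, and the others follow from their sample sizes. The relative reading of the headline 25% conflicts with n = 53. This stands for the examples. It does not settle the general rule once the null moves, because the same paragraph uses the relative scale for its own 40% baseline.

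A reader might infer that the stage tests are underpowered or that 250 is too few. The documents do not support that. They give no stage mix, so the actual power of each stage test cannot be computed, and the small groups in Step 3 are assumptions. Sizes that are sufficient can fit: one group of 69 and three of 43 make 69 + 3 × 43 = 198, within 250. Nor are 43, 44, 39 and 69 strict minimums, since some smaller sizes also reach 80%.

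A reader might also infer that the relative reading is always out of reach. It exceeds enrolment at a 40% baseline, narrowly, but not at 50%.

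Finally, section 1.3 describes the study as estimating an effect size, which lowers the stakes. Section 6.2.1 nevertheless bases the sample size on these tests.

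**Conclusion.** The point holds as a fault of statement, and it should be fixed. The plan's sample sizes reproduce, but the unconditional 80% floor does not follow from them. It depends on group sizes that the plan neither projects nor secures, and it fails in small groups and for the plan's own 40% to 60% case at the standard size of 53. The smoking cessation test uses the whole sample and is unaffected (60 to 75 at n = 250 has 99.7% power).

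The mixed scale leaves the target undefined after the null is reset. At a 40% baseline the two readings differ about sixfold in required size, and the statement that 250 suffices is true under only one of them.

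These results treat the Months 1-8 rate as a fixed, known null, as the plan does. They do not show that any group will fall short.

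**What to change.** In section 6.2.1:

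1. Replace the unconditional floor with: power of at least 80% is assured once the group reaches the n for its null and target rate (50 to 75: 43; 40 to 65: 44; 60 to 85: 39; 40 to 60: 69), and may be lower in smaller groups. Note that, because exact power is saw-toothed, 80% is first reached with equal tails at 40, 42, 36 and 67.
2. Write every effect as baseline rate to target rate on one scale, and state the target that applies after the null is reset.
3. Name the two-sided exact convention.
4. Make the statement that 250 suffices conditional on the size of each stage group, and give the expected size of each.
5. Correct the power for n = 32 (60 to 90) to 90.6%.

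The cost is wording and a short table. The stated power becomes less favourable. No patients are added, and neither the design nor the test changes.

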6.3 Analyses Plans

6.3.1 Primary Analysis (or Analysis of Primary Endpoints)

The major focus of the trial analysis will be to determine if there is a statistically discernible effect for the decision aid in influencing practice patterns before and after implementation of the decision aid. The rates of NCCN adherence by stage will be an important covariate. The current sample size now reflects the ability to detect a moderate effect size for decision aid interactions with outcomes. More detailed analysis to correlate correlations between changes in practice patterns to other variables will be carried out with logistic regression, with special modifications for patient sociodemographic and clinical characteristics (e.g., nodes, tumor size, histology).

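### Section 6.2.1 measures improvement on two scales, prints no target for the headline 25%, and promises an 80% power floor that does not hold for every stage size and target

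*Combined protocol and SAP*

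**What the plan says.** All the sample-size reasoning is in section 6.2.1 of the combined protocol and SAP.

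- **Headline effect.** For each disease stage there will be "a test of at least a 25% improvement using the decision aid compared with the pre-intervention results". No target rate is printed, and nothing says whether 25% is relative or in percentage points.
- **Test and size.** "Based upon the one-sample binary exact test with power set at 90" per cent and "a 2-sided type I error of 0.017 (adjusted for up to 3 tests for all patients), 53 patients would be required for each test", with a 50% null that is to be replaced by the rate found in Months 1-8.
- **Adjuvant chemotherapy example, 40% baseline.** "a test to detect a 50% improvement to 60% will require 70 patients with 80% power and 88 patients with 91% power". This is the only effect given with both its baseline and its target.
- **Smoking cessation example, 60% baseline.** "a 50% improvement will require 32 patients with 92% power, but a 15% improvement with 90% power requires 135 patients".
- **Power floor.** For any individual test the size may differ from 53, and "the null hypothesis may differ from 50% and result in reduced power but will be at least 80" per cent. On size, "The test would reflect the actual accrual by stage with the use of the decision aid"; no minimum and no expected stage split are given.

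The section concludes that no comparison is expected to need more than the 250 patients to be enrolled. Section 6.3.1 adds only that "The current sample size now reflects the ability to detect a moderate effect size for decision aid interactions with outcomes", which gives neither a target nor a scale.

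**The concern.** The one fully specified effect, 40% to 60%, is labelled a 50% improvement, so the scale the text shows is relative. A reader who carries that scale to the other figures takes 15% from 60% to mean 69%, and 25% from 50% to mean 62.5%. The stated sizes do not give about 90% power for either.

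The ambiguity also affects how the plan would be carried out, because the null is to be updated from the pre-intervention data. If the observed baseline were 40%, a 25% improvement could mean a target of 65% or of 50%. At 53 patients those have 87.2% and 13.6% power.

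The power floor is a separate problem. An unconditional statement of at least 80% power invites a reader to treat a non-significant result in a small stage group as evidence of no change, when the test may have had little chance of detecting one.

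**Working it through.** **Inputs, all from section 6.2.1:** one-sample exact binomial test; two-sided alpha 0.017, taken here as 0.0085 per tail; nulls of 50%, 40% and 60%; sizes 53, 70, 88, 32 and 135; total enrolment 250.

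**Formula.** For size n and null p0, let c be the smallest count with P(X ≥ c | n, p0) ≤ 0.0085. Power at target p1 is P(X ≥ c | n, p1); the lower rejection region adds nothing material for these targets.

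**Step 1: candidate targets.**
- 50% from 40%: relative 0.40 × 1.50 = 0.60, as printed; in points it would be 90%.
- 50% from 60%: relative 0.60 × 1.50 = 0.90; in points 0.60 + 0.50 = 1.10, which is impossible.
- 15% from 60%: relative 0.60 × 1.15 = 0.69; in points 0.75.
- 25% from 50%: relative 0.50 × 1.25 = 0.625; in points 0.75.

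**Step 2: reproduce the stated figures.**

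| n | Label in plan | Stated power | Reading | c | Exact power |
|---|---|---|---|---|---|
| 70 | 50% | 80% | 40→60, relative (printed) | 39 | 80.4% |
| 88 | 50% | 91% | 40→60, relative (printed) | 47 | 91.4% |
| 32 | 50% | 92% | 60→90, relative | 27 | 90.6% |
| 135 | 15% | 90% | 60→75, points | 95 | 90.8% |
| 135 | 15% | 90% | 60→69, relative | 95 | 40.5% |
| 53 | 25% | 90% | 50→75, points | 36 | 90.8% |
| 53 | 25% | 90% | 50→62.5, relative | 36 | 25.3% |

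All five sizes reproduce to within 2 points of power, but only if 50% is relative and 15% and 25% are in points. A relative 15% from 60% would need about 386 to 400 patients for 90% power, and all 250 give 71.0%. A relative 25% from 50% would need about 214 to 223. Changing the test does not rescue the relative 15%: about 328 or more patients at one-sided 0.017, about 298 to 317 at two-sided 0.05, and 759 per group for a two-sample comparison.

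**Step 3: the 80% floor.** Take the more favourable reading, +25 points.

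| n | 30→55 | 40→65 | 50→75 |
|---|---|---|---|
| 30 | 64.5% | 65.5% | 67.4% |
| 40 | 78.7% | 79.8% | 82.1% |
| 53 | 90.0% | 87.2% | 90.8% |

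Exact power moves up and down as n grows because c is a whole number. For 50→75 it first reaches 80% at n=40, drops to 76.6% at n=42, and stays at or above 80% from n=43. For baselines of 40% and 30% it stays there from n=44 and n=45. The 30 and 40 rows are illustrative, since the plan gives no stage sizes. As a share of enrolment, 40/250 = 16%.

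For the plan's own 40→60 example, power is 43.1% at n=30, 56.8% at n=40 and 64.5% at n=53; it first reaches 80% at n=67.

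**Step 4: sensitivity to the form of the exact test.** A minimum-likelihood two-sided rejection region gives the same powers for every row in Step 2. It changes 40→60 at n=53 to 74.2%, and the first size reaching 80% to 63. Neither change restores the floor.

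**The case against.** The best counter-reading is a single misprint. 60% to 75% is also a 25% relative gain (0.75/0.60 = 1.25), so if 15% was a slip for 25%, every worked example sits on one relative scale, with 50% to 75% being a 50% gain. The documents do not rule this out. It still leaves a wrong printed figure, and it makes the headline worse: a relative 25% from the 50% null has 25.3% power at 53 patients. The points reading of the headline therefore remains an inference from n=53.

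On the floor, one can say that it is a planning criterion, since the 40% to 60% example that follows it lets the size rise to keep 80%. It is also true that, at 53 patients and +25 points, power is 90.0%, 87.2%, 90.8%, 95.4% and 99.5% for baselines of 30% to 70% in steps of 10, so a changed baseline alone does not break the floor on that reading. Both points are fair. But the text says that size follows accrual and sets no minimum, so nothing secures the criterion.

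Finally, section 6.3.2 puts effect sizes and 95% confidence intervals ahead of p-values, which softens the risk of over-reading a non-significant result. That sentence stands in the secondary-analysis section, so its reach to the primary tests is arguable. The gap between 92% and 90.6% at n=32 is trivial.

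**Conclusion.** The concern holds on three counts.

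1. The 50% and 15% improvements, as printed in one sentence, cannot share a scale.
2. The headline 25% has neither a target nor a scale. The plausible readings differ between 90.8% and 25.3% power at 53 patients; the 15% figure differs between 90.8% and 40.5% at 135. The conclusion that 250 patients suffice holds for 15 points but not for a relative 15%.
3. The unconditional 80% floor is false as written. The plan's own 40% to 60% example contradicts it at 53 patients without any assumption about stage sizes, and at 50% to 75% any group under 40 falls below it.

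The figures assume the stated exact test with equal tails at two-sided 0.017 and a fixed null. No actual shortfall in any stage is shown, because no stage split is given. The underlying calculations are sound once the targets are known; the text that describes them should be corrected.

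**What to change.** In section 6.2.1:

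- Print baseline, target, difference in points and power beside each size: 53 for 50% to 75% (+25, 90.8%), if the sponsor confirms that target; 70 and 88 for 40% to 60% (+20, 80.4% and 91.4%); 32 for 60% to 90% (+30, 90.6%); 135 for 60% to 75% (+15, 90.8%).
- Name one scale for the headline 25%, and describe the test as one of no change from the pre-intervention rate, powered for the stated target.
- State which effect, on which scale, applies once the baseline is updated from Months 1-8.
- Limit the 80% statement to the combinations of size, baseline and target where it holds. At +25 points that means stage groups of at least 45, 44 and 43 patients for baselines of 30%, 40% and 50%. Say that smaller groups have less power.
- If a relative effect was meant, restate the power: about 25% at n=53 for a relative 25% from 50%, and about 41% at n=135 for a relative 15% from 60%. If 15% was a misprint for a relative 25%, correct the label; 90.8% at n=135 then stands.

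The cost is a few sentences and the sponsor's statement of the intended effect and scale. Enrolment, alpha and the test stay as they are.

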6.2.2 Accrual estimates

The total number of participants to be enrolled is 250. The expected number of participants to be enrolled per quarter is 60-65

6.3 Analyses Plans

6.3.1 Primary Analysis (or Analysis of Primary Endpoints)

The major focus of the trial analysis will be to determine if there is a statistically discernible effect for the decision aid in influencing practice patterns before and after implementation of the decision aid. The rates of NCCN adherence by stage will be an important covariate. The current sample size now reflects the ability to detect a moderate effect size for decision aid interactions with outcomes. More detailed analysis to correlate correlations between changes in practice patterns to other variables will be carried out with logistic regression, with special modifications for patient sociodemographic and clinical characteristics (e.g., nodes, tumor size, histology).

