3.2.1 Inclusion Criteria

1. Over age of 18

2. Able to provide informed consent
3. Able to use a web-based interface
4. Histologically proven or clinically apparent diagnosis of non-small cell lung cancer. Eligible NSCLC histological types include:
 - Adenocarcinoma
 - Squamous Cell Carcinoma
 - Large Cell Carcinoma
 - Adenosquamous Carcinoma
5. Newly diagnosed, with new primary occurrence of NSCLC, or diagnosed with a new recurrence or new progression of existing disease, and not yet treated for the new problem.
6. Being seen in consultation at the UCSF thoracic oncology clinics

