6.1.1 Study Design

This study involves the evaluation of the decision support tool Patients with Power, previously used with breast cancer patients, in the non-small cell lung cancer patient population.

1. Characterize physician and patient populations and treatment decisions in the UCSF thoracic oncology practices.
2. Establish the acceptability, feasibility, and effectiveness of a novel decision aid for decisions made about treatment for NSCLC.
3. Conduct an evaluation of changes in NCCN-guided practice patterns before and after implementation of the decision aid, with respect to 6 clinical scenarios:

All patients: if smoking cessation intervention is provided at initial visit;

Stage IB-IIB patients receiving surgery: if adjuvant chemotherapy is given after surgery;

Stage III patients receiving surgery: if pathologic staging of mediastinal nodal disease is done prior to initiation of therapies;

Stage III patients not receiving surgery: if pathologic staging of mediastinal nodal disease is done prior to initiation of therapies;

Stage III patients not receiving surgery: if concurrent chemoradiation is given upfront;

Stage IV patients: if molecular testing is done prior to initiation of systemic therapy.

4. Collect data to facilitate the design of future larger-scale evaluations, including assessments of physician-patient agreement and patients' levels of decisional conflict and satisfaction with decisions made as well as potential correlations to patient-reported quality to life.

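### The primary tests compare crude before and after rates, and the planned regression does not define a case-mix-adjusted period effect on which the primary conclusion rests

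*Combined protocol and SAP*

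**What the plan says.** Section 6.2.1 sets the primary test: "Based upon the one-sample binary exact test with power set at 90% and a 2-sided type I error of 0.017". The sample size starts from "assuming a null hypothesis of 50% in the pre-intervention cohort" and leads to "53 patients would be required for each test". The null is then replaced by the observed baseline: "This estimate for the null hypothesis will be modified using the results obtained prior to use of the decision aid (Months 1-8". No covariate enters this test.

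Some metrics pool sub-groups. The second is "Stage IB-IIB patients receiving surgery: if adjuvant chemotherapy is given after surgery", so IB, IIA and IIB form one proportion. The sixth, molecular testing in stage IV, covers every eligible histology; section 3.2.1 lists four types under "Eligible NSCLC histological types include". The first, smoking cessation, covers all stages.

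The two cohorts arise differently. Section 3.5 takes the baseline from observed new-patient visits and chart review. The aid cohort must consent, be able to use a web interface and complete questionnaires (sections 3.2 to 3.2.2), with 30% expected to be lost to refusal, dropout or ineligibility (section 6.2.1).

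Section 6.3.1, headed as the primary analysis, says that adherence by stage will matter as a covariate. It continues: "More detailed analysis to correlate correlations between changes in practice patterns to other variables will be carried out with logistic regression", allowing for sociodemographic and clinical characteristics with nodes, tumour size and histology as examples.

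**The concern.** A one-sample test against a single number cannot tell a change in practice from a change in who was seen. If the chance of a yes differs between IB and II, or between histologies, a different mix in the aid period moves the crude rate even when the aid does nothing. The plan's own choice of covariates shows that it regards such characteristics as relevant.

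The regression sentence is about relating changes to other variables. It does not name a pre/post term, a covariate list for each metric, or the weight its result carries. Section 6.3.2 also lets multivariable models be built partly on statistical criteria, so the model is not fixed in advance. At stake is whether a significant result on a metric can be attributed to the aid, and whether a real gain could be missed.

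**Working it through.** **The plan's own figures.** Exact binomial, 0.017/2 = 0.0085 per tail.
- Null 50%, true 75%, n=53: reject upward at 36 or more; power 90.8%. The stated 53 reproduces, reading the 25% improvement as 25 points.
- Null 40%, true 60%: reject at 39/70 (power 80.4%) and 47/88 (power 91.4%). Stated: 80% and 91%.

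These figures all use crude rates and treat the null as known.

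**False improvement, adjuvant chemotherapy metric.** From the plan: the 40% baseline example, n = 53, 70 and 88, and the test. Assumed: two sub-groups mixed 50:50 at baseline, and no effect of the aid. Let *g* be the gap between sub-group rates and *s* the shift in mix towards the higher-rate group. Then

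crude aid-period rate = 0.40 + *s* × *g*.

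For example, sub-group rates of 20% and 60% (*g* = 0.40) at a mix of 30:70 (*s* = 0.20) give 0.30 × 0.20 + 0.70 × 0.60 = 0.48. The rejection limits are 31/53, 39/70 and 47/88. The chance of reaching them is:

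| Shift *s* | Gap *g* | True crude rate | n=53 | n=70 | n=88 |
|---|---|---|---|---|---|
| 0 | any | 40% | 0.5% | 0.6% | 0.7% |
| 5 points | 20 points | 41% | 0.8% | 0.9% | 1.3% |
| 10 points | 20 points | 42% | 1.1% | 1.4% | 2.0% |
| 10 points | 40 points | 44% | 2.4% | 3.2% | 4.8% |
| 20 points | 40 points | 48% | 8.2% | 12.1% | 18.2% |

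The nominal upper tail is 0.85%. A 20-point shift with a 20-point gap gives the same 44% as the fourth row. If the sub-group counts are held fixed instead of varying at random, the last row becomes 6.5%, 10.3% and 17.4%; the conclusion is the same.

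**Masking.** Assume a true gain of 20 points in each sub-group (20% and 60% become 40% and 80%) and a shift towards the lower-rate group.
- Mix unchanged, crude rate 60%: power 80% (n=70), 91% (n=88).
- Lower-rate share 60%, crude rate 0.60 × 0.40 + 0.40 × 0.80 = 56%: power 57%, 73%.
- Lower-rate share 70%, crude rate 0.70 × 0.40 + 0.30 × 0.80 = 52%: power 31%, 44%.

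**Molecular testing metric.** Assume that 90% of non-squamous and 30% of squamous patients are tested. A squamous share of 25% gives 0.75 × 0.90 + 0.25 × 0.30 = 75%. A share of 15% gives 0.85 × 0.90 + 0.15 × 0.30 = 81%, and false improvement of 4.7% (n=53) to 12.3% (n=88). A share of 20% gives 78%, and 1.5% to 3.4%. No input here comes from the documents except the test.

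**Power of a pre/post contrast.** For 40% against 60%, two-sided 0.017, equal periods (assumed), normal approximation:

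n per period = [2.387 × √(2 × 0.5 × 0.5) + z × √(0.24 + 0.24)]² / 0.20².

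- z = 0.842 (80% power): (1.688 + 0.583)² / 0.04 = 129.
- z = 1.282 (90% power): (1.688 + 0.888)² / 0.04 = 166.

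With 70 per period, the standard error is √(0.48/70) = 0.0828, and power is Φ(0.20/0.0828 − 2.387) = 51%. With 88 per period, it is Φ(0.20/0.0739 − 2.387) = 63%.

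**The case against.** Adjustment is not absent. Stage as a covariate and the logistic regression both stand under the primary analysis heading in section 6.3.1, not in section 6.3.2. Five of the six metrics are restricted to a stage or stage group, so most between-stage confounding is already removed from them. A reader might infer that the plan ignores case mix or relegates it to secondary analysis; the documents do not support that. What stands is narrower: the regression has no defined period effect, covariate set or role, and stage restriction does not deal with mix inside a metric or with the all-stage smoking metric.

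The shifts are also assumed. Nothing in the documents points to a 20-point change in mix between adjacent periods in the same clinics, and for small shifts the inflation is slight. This objection stands in full as to size, so the 18% is one corner of a range and not a forecast.

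Section 1.3 describes a study meant to estimate an effect size for later work, where a crude test followed by regression is a common choice. That lowers the urgency, but section 6.2.1 still attaches formal error rates to these tests.

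**Conclusion.** The concern holds for the adjuvant chemotherapy and molecular testing metrics, and for stage mix in the smoking metric. The tests that carry the 0.017 level are unadjusted, and the planned regression is not specified as an adjusted before/after contrast. With a 40% null and 53 to 88 patients, false improvement runs from about 1-2% (10-point shift, 20-point gap) through 2-5% (10-point shift, 40-point gap) to 8-18% (20-point shift, 40-point gap), against a nominal 0.85%. A shift the other way costs power. All of this rests on assumed rates and mixes.

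Two further inferences are tempting. One is that the stage III metrics share the problem to a similar degree; the documents give no sub-group rates for them, and nothing was calculated here. The other is that adjustment would make the before/after comparison free of bias. It would remove measured case mix only; secular trend and selection by consent and web ability would remain.

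**What to change.** In section 6.3.1:
- Name the period (pre/post) term of a logistic model, fitted to pooled months 1-8 and aid-period patients, as the adjusted before/after contrast for each affected metric, and say that the primary conclusion is read with it.
- Use one fixed stratifier per metric: sub-stage for adjuvant chemotherapy, histology group for molecular testing, stage for smoking cessation.
- State a rule for merging sparse strata.
- Report the crude one-sample test alongside.

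In the months 1-8 data collection, require the same stratifiers to be abstracted from the records; the documents do not say that they are.

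In section 6.2.1, state the power of the adjusted contrast separately. The period term carries the baseline's sampling error, so the figures of 70 and 88 do not transfer: the unadjusted approximation above gives about 129 and 166 per period for 80% and 90% power. Testing the aid-period rate against a mix-standardised baseline is not an equivalent shortcut, because it treats the baseline as known.

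The cost is SAP wording, some abstraction for the baseline cohort, and an honest statement of lower power.
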